- 6) Patients whose Mini-Mental State Examination (MMSE) scores were less than 24.
- 7) Patients who had medical history that did not fit to exercise, such as orthopedics diseases or cardiopulmonary dysfunction.
- 8) Patients who received education less than 6 years.
- 9) Patients who could not walk and live independently.
- 10) Patients who received brain surgery (e.g. deep brain stimulation);
- 11) Patients whose exercise length longer than 50 minutes per week.

All participants were fully informed and signed written consent forms. This study was approved by the ethic committee of Ruijin Hospital affiliated to Shanghai Jiao Tong University School of Medicine.

2. Randomization, Blinding and Follow-Up

There was no randomization adopted. Assessments were done at baseline and the three follow-ups (Nov. – Dec. 2019, Oct. - Nov. 2020 and Jun. – July 2021). We also monitored the frequency and lengths of Tai Chi exercise for each patient. Patients whose training were less than 60 minutes per time or less than twice per week were regarded as giving up training. The flow chart of recruitment and follow up was shown in Part II.

PD patients who did not receive Tai Chi training were matched to Tai Chi training PD patients with similar age, sex, disease duration and initial Hoehn - Yahr staging by propensity score matching methods. They also received evaluation at baseline and three follow-ups (Nov. – Dec. 2019, Oct. - Nov. 2020 and Jun. – July 2021).

Since this is an interventional study of movement, we cannot perform the blinding on patients. Thus, the assessors and the statisticians were blinded to study design. The ethic committee monitored the whole process of blinding. Patients were demanded not to tell their group assignments to the assessors.

3. Exercise Interventions and Quality Control

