5.2 Secondary Outcomes

The secondary outcomes were annual change of the following indicators except the need of increasing antiparkinsonian therapies which were analyzed by survival analysis:

- (1) the change of LEDD⁴
- (2) the need of increasing antiparkinsonian therapies, including both the need of increasing antiparkinsonian drugs and the need of surgery, such as DBS or lesion surgery.
- (3) Motor evaluations: UPDRS part III as overall motor evaluations; TUG and BBS.
- (4) Other non-motor symptoms, including autonomic function, mood, sleep and cognition, assessed by rating scales.
- (5) Quality of life: PDQ-39;
- (6) the difference of prevalence of complications (dyskinesia, on-off phenomenon, dystonia, PD-MCI, hallucinations, restless legs syndrome).

NOTE: We consider the following aspects as the evidences for delaying disease progression:

- (1) the annual change of UPDRS total score;
- (2) the annual change of LEDD;
- (3) the need of increasing antiparkinsonian therapies.

6. Statistical Analysis

R (version 3.5.1) and RStudio (version 1.1463) were used to perform statistical analysis.

Packages stats (version 3.5.1), base (version 3.5.1), spinds (version 2.2.0), lars (version 1.2), nlme (version 3.1-145), plyr (version 1.8.5), PGEE (version 1.5), ggplot2 (version 3.2.1), survival (version 2.43-3) and survminer (version 0.4.3) were introduced into statistical analysis. Figures were plotted in Prism 9 (version 9.3.1, San Diego, CA).

All analysis about primary and secondary outcomes were conducted on an intention-to-treat basis. Analysis of variance (ANOVA) were used in comparing at numerical demographic information. Pearson Chisq-Square test or Fisher test were used in analysis at categorical demographic information. Shapiro-Wilk normality test was used to assess the normality of variables. Independent-sample t-tests (with 95% confidence intervals) were used to compare group means. Data were presented in the way of between-group differences. The longitudinal effects of self-changes were calculated using repeated measures ANOVA.

We built a cohort which started enrollment since 2016, then more patients were enrolled gradually into another 4 classes (2nd Class: start from Nov. 2016; 3rd Class: start from Mar. 2017; 4th Class: start from Sept. 2017; 5th Class: start from Jan. 2018). All the patients in those 5 classes were trained continually and has been received assessment in the follow-up of 2019, the follow-up of 2020 and the follow-up of 2021.

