We set the rate of UPDRS total score change (per year) as the primary outcome. As for the secondary outcomes, UPDRS part III, other motor evaluations (TUG and BBS), evaluations of non-motor symptoms (autonomic function, mood, sleep, and cognition, assessed by rating scales), quality of life evaluated by PDQ-39, the change of LEDD, and the difference of prevalence of complications (dyskinesia, on-off phenomenon, dystonia, PD-MCI, hallucinations, restless legs syndrome). We also observed the need for increasing antiparkinsonian therapy, including increasing antiparkinsonian drugs, and deep brain stimulation (DBS). LEDD of patients who received DBS were not taken into account.

We make the comparisons between the patients who received Tai Chi training and patients who did not receive Tai Chi training as controls. Analyses of the adjusted means of change from baseline to each follow-up in rating scales were done with logarithmic linear model of covariance that included the following fixed effects: treatment group

(Tai Chi = 1, control group = 0), months in this trial, the changed amount of LEDD and baseline Hoehn-Yahr score. Years of education were also included when analyzing PDCRS. We calculated the *p* value with the bootstrap method for resampling 1000 times. To demonstrate the results, mean change with its 95% confidential intervals (CIs) was introduced. Kaplan Meier plot with table of number at risk was introduced. Bonferroni correction was introduced.

7. Safety Reporting: Adverse events (AEs) and serious adverse events (SAEs)

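### Need for increased therapy has no specified between-group estimate, no model adjustment beyond four-factor matching and no event-date rule, so its survival curves can carry baseline or entry-date differences

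*Combined protocol and SAP*

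**What the plan says.** Section 5.2 sets this outcome apart from the other secondary outcomes, which are analysed as annual change: "the need of increasing antiparkinsonian therapies which were analyzed by survival analysis". It is a composite, "including both the need of increasing antiparkinsonian drugs and the need of surgery, such as DBS or lesion surgery". The note closing Section 5.2 gives it special weight, listing it third under "We consider the following aspects as the evidences for delaying disease progression", beside annual change in UPDRS total score and in LEDD.

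Section 6 lists software ("survival (version 2.43-3) and survminer (version 0.4.3) were introduced into statistical analysis") and one display: "Kaplan Meier plot with table of number at risk was introduced". Its covariate model has a limited scope: "Analyses of the adjusted means of change from baseline to each follow-up in rating scales were done with logarithmic linear model of covariance". That model includes group, months in the trial, change in LEDD and baseline Hoehn-Yahr score.

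Section 2 says that there was no randomisation and that controls were matched by propensity score on four factors. On timing it says: "Assessments were done at baseline and the three follow-ups", the follow-ups being calendar rounds in late 2019, autumn 2020 and mid-2021. The Tai Chi classes start from 2016 onwards. Control entry dates are not given.

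**The concern.** A Kaplan-Meier plot describes two groups. It yields no between-group estimate and adjusts for nothing. In a randomised trial the second point would matter little. Here the only protection is matching on four factors, and neither baseline LEDD nor baseline UPDRS is among them. Both plausibly predict when treatment is next increased. If they differ between groups, the curves separate without any effect of Tai Chi.

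The second issue is timing. Follow-up rounds fall on fixed calendar dates while patients enter over two to three years, so time from entry to a given round depends on entry date. If a therapy increase were dated to the round at which it came to light, its recorded time would partly measure when the patient joined. Matching does not cover entry date, and the months-in-trial covariate is confined to rating scales.

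At stake is one of the three legs of the delayed-progression claim.

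**Working it through.** **No figure to reproduce.** The documents give no sample size, event count, alpha, hazard ratio or power for this outcome. The check is therefore a simulation with no true effect (HR = 1, exponential event times, two-sided log-rank at 5%).

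**From the documents:** class starts in Section 6 (2016, taken as January; Nov 2016; Mar 2017; Sept 2017; Jan 2018) and the three follow-up windows in Section 2.

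**Assumed:** numbers per arm, annual event hazard (0.10 or 0.25), control entry dates, confounder strength, and the log-rank test itself, which the plan does not name.

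**Step 1: time from entry to first follow-up.** Taking the middle of the Nov-Dec 2019 window, the five classes wait about 47, 37, 33, 27 and 23 months. The later gaps are about 11 and 8 months. Two patients who each need more therapy 12 months after entry would, under visit dating, be recorded at 47 months (class 1) and 23 months (class 5).

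The Overview has classes beginning as late as Jan 2019. Counting to the window's opening in Nov 2019, the shortest wait is 22 months from Jan 2018 but 10 months from Jan 2019.

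**Step 2: unmatched prognostic factor, true event dates, same entry dates in both groups.** 600 runs per cell; Monte Carlo SE = √(0.05 × 0.95 / 600) = 0.9 points. n = 60, 120 or 200 per arm; five of the six n/hazard settings completed.

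| Factor (prevalence Tai Chi vs control) | Unadjusted | Stratified on the factor |
|---|---|---|
| HR 1.5, 40% vs 50% | 4-7% | 4-6% |
| HR 2, 30% vs 50% | 7-17% | 4-7% |

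As a continuous example, a 0.3 SD imbalance with HR 1.5 per SD gives a spurious HR of exp(-0.3 × ln 1.5) = 0.885. The corresponding false-positive rate was about 5-12%.

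**Step 3: events dated to the visit that reveals them.** 400 runs per cell; SE = √(0.05 × 0.95 / 400) = 1.1 points near 5%. n = 60-100 per arm. The mean class start, in months after Jan 2016, is (0 + 10 + 14 + 20 + 24) / 5 = 13.6.

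| Control entry | Mean shift from 13.6 | False-positive rate |
|---|---|---|
| Same as classes | 0 | 4-6% |
| Uniform over 24 months (mean 12) | 1.6 months earlier | 4-6.5% |
| 3 months later | 3 | 5-12% |
| 6 months later | 6 | 8-11% at hazard 0.10; up to 27% at 0.25 |
| All with class 5 (month 24) | 24 - 13.6 = 10.4 later | from 18% at hazard 0.10; about 70% at 0.25 with n = 100 |

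In the last two rows nearly all false positives favour Tai Chi. The direction depends on who enters later: with all controls entering in Jan 2016, the error runs against Tai Chi.

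**Step 4: same entry patterns, true event dates.** The false-positive rate stays at about 3-7% whatever the control entry pattern. With a constant hazard, entry date does harm only through the dating rule.

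**The case against.** The strongest reply is that this is under-specification, not a demonstrated bias. Section 5.2 does say survival analysis, and the listed packages can run a log-rank test or a Cox model. The groups are matched on four relevant factors, so calling the comparison simply unadjusted would be wrong. Nothing in the documents shows an imbalance in baseline LEDD or UPDRS. The confounding effect is modest, and with the milder assumed factor it cannot be told from 5%. A plot has no false-positive rate, so the figures describe a test that the plan never names. All this stands, and it limits the size of the point. It does not remove it: a package list fixes neither a test nor a covariate set, and the plan adjusts its rating scales but not this outcome.

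A reader might also infer that events are seen only at the study visits and that their wide spacing creates a false difference. The documents support neither step. The assessments in Section 2 can be read as the clinic rating scales in Section 4, and a prescription change or operation can have its own date. Spacing alone leaves the error at 4-6%. Nor does every difference in entry dates matter: entry spread over 24 months with a similar mean gives 4-6.5%. A clear shift in mean entry is needed, and the documents do not say that there was one.

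**Conclusion.** The point holds as a gap in the analysis of an outcome that carries part of the main claim. No between-group estimate is specified, there is no model adjustment beyond four-factor matching, and there is no event-date rule. In a non-randomised comparison this leaves room for bias that baseline data the trial already needs could reduce.

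The size is conditional. Unmatched factors of the assumed strength give a false-positive rate of about 4-17%. Visit dating together with a shift in mean entry gives about 8-27% (6 months) or 18-70% (all controls with class 5) for 60-100 per arm and hazards of 0.10-0.25 per year. The class 5 case is an extreme that nothing in the text supports; it marks an upper end, not an expectation. The documents do not show that events were dated to visits, that entry dates differed, or that the result is false. The plan simply does not exclude these possibilities.

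**What to change.** 1. State the time origin, the source of the event date and the censoring rule for this outcome.
2. Make the inferential analysis a Cox model with arm, baseline LEDD, baseline UPDRS and entry date (or class). Add the four matching factors as far as the event count allows. Cluster the variance on matched set where sets can be identified. Report the hazard ratio with its 95% CI.
3. Use actual prescription or surgery dates where they are available. Where only the revealing visit is known, use an interval-censored or discrete-time (complementary log-log) model.
4. Keep the Kaplan-Meier plot and number-at-risk table as description.
5. Reconcile the last class start (Jan 2018 in Section 6, Jan 2019 in the Overview), which sets the shortest time to first follow-up at about 22 or about 10 months, and report control entry dates.

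The cost is a few sentences of analysis plan, a little more analysis work and a record look-up for event dates. The survival package is already listed, and baseline UPDRS and LEDD are already needed for the change outcomes. Whether prescription records and matched-set identifiers are available is not documented, so the look-up effort is uncertain.

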5.1 Primary Outcome

The primary outcome was the annual change of UPDRS total score measured in “ON” state at three follow-ups.

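### Holm's step-down procedure should replace single-step Bonferroni: same family-wise error guarantee, never fewer rejections, and a gain that is useful when several effects are real and nil when only one is

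*Combined protocol and SAP*

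**What the plan says.** Section 6 (Statistical Analysis) closes with "Bonferroni correction was introduced". It attaches no family, number of tests or alpha, and does not say whether the primary outcome is inside the correction. No reason is given for the single-step method.

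The surrounding text shows that many hypotheses are in play:

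- The primary outcome, the annual change in UPDRS total (Section 5.1), is measured in the ON "state at three follow-ups".
- Section 5.2 adds a long list of secondary outcomes, analysed as annual changes "except the need of increasing antiparkinsonian therapies which were analyzed by survival analysis". It also lists six complication prevalences.
- A note in Section 5.2 singles out three outcomes: "We consider the following aspects as the evidences for delaying disease progression". They are UPDRS total, LEDD and the need for more antiparkinsonian therapy.

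On the tests themselves, Section 6 says "Independent-sample t-tests (with 95% confidence intervals) were used to compare group means". It later says "Analyses of the adjusted means of change from baseline to each follow-up in rating scales were done with logarithmic linear model of covariance", with the p "value with the bootstrap method for resampling 1000 times". The bootstrap sentence sits in the paragraph on the rating-scale models. The documents do not state what unit is resampled, whether the resamples are centred on the null, or whether one set of resamples serves all outcomes.

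**The concern.** Bonferroni compares every p value with alpha/m. Holm makes that comparison only for the smallest p value. After each rejection the divisor falls by one, so later p values face alpha/(m-1), alpha/(m-2), and so on. Both methods hold the family-wise error at or below alpha without any assumption about how the outcomes are related. In testing terms, single-step Bonferroni therefore gives up rejections that the same error guarantee would allow.

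This matters most where the plan draws one conclusion from several outcomes together. The three outcomes in the Section 5.2 note are such a case: the claim of delayed progression is strongest if all three are supported, and that is where a step-down method helps most.

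**Working it through.** **Inputs.** The documents give no figure to reproduce. The following is taken or assumed:

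- Alpha: not stated. Two-sided 0.05 is assumed, from the 95% intervals in Section 6.
- Family size m: not stated. The smallest plausible family is 3 (the three outcomes in the note, or one outcome at three follow-ups). From Sections 4, 5 and 6 I count 16 outcomes: UPDRS total, UPDRS III, TUG, BBS, NMS-Quest, SCOPA-AUT, HAMA, HAMD, PDSS, ESS, RBD-HK, MMSE, PDCRS, PDQ-39, LEDD and therapy need. The six complications make 22. Testing each at three follow-ups gives at most 16 × 3 = 48 or 22 × 3 = 66.
- Effect size: assumed to give 80% power at unadjusted 0.05, so the expected test statistic is 1.96 + 0.84 = 2.80.
- Correlation between outcomes: assumed 0.3 to 0.5.

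**Step 1: validity of Holm.** Suppose m0 of the m nulls are true. When Holm first rejects a true null, all m0 true nulls are still in play, so the threshold in force is at most alpha/m0. The chance that any of the m0 true-null p values falls below alpha/m0 is at most m0 × alpha/m0 = alpha, whatever their dependence. Every Holm threshold is at least alpha/m, so nothing that Bonferroni rejects is lost.

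**Step 2: what Bonferroni costs per test.** Power is approximately Φ(2.80 - c), where c is the two-sided critical value at 0.05/m.

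- m = 3: 0.05/3 = 0.0167, c = 2.39, power 0.66.
- m = 16: 0.05/16 = 0.0031, c = 2.96, power 0.44.
- In the same way: 0.40 at m = 22, 0.32 at m = 48 and 0.29 at m = 66.

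**Step 3: what Holm gives back.** Simulation with equicorrelated normal statistics, 100,000 draws per main scenario:

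| Scenario | Quantity | Bonferroni | Holm |
|---|---|---|---|
| m = 3, all real | average power, correlation 0.3 and 0.5 | 0.66 | about 0.74 |
| m = 3, all real | all three detected, correlation 0.3 | 0.36 | 0.55 |
| m = 3, all real | all three detected, correlation 0.5 | 0.42 | 0.59 |
| m = 3, all real | at least one rejection, correlation 0.3 | 0.911 | 0.911 |
| m = 16, 8 real | average power, correlation 0.3 and 0.5 | 0.44 | 0.47 |
| m = 16, 8 real | family-wise error on the unaffected outcomes | 0.02 | 0.03 |
| m = 3, one real | power | 0.66 | 0.66 |
| m = 16, one real | power | 0.44 | 0.44 |

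The chance of at least one rejection cannot differ, because Holm's first step uses alpha/m as Bonferroni does.

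**Step 4: does the gain grow with m?** With all effects real and correlation 0.5, average power goes from 67% to 74% (m = 3), 44% to 55% (16), 40% to 50% (22), 32% to 40% (48) and 28% to 35% (66). The gains are 7, 11, 10, 8 and 7 points. What grows steadily is Bonferroni's loss against no adjustment: from 80 - 66 = 14 points at m = 3 to 80 - 29 = 51 at m = 66. Holm returns only part of that.

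**Step 5: bootstrap resolution.** If p is computed as (b + 1)/(B + 1) with B = 1000, the smallest possible p is 1/1001. After multiplication by m this is 16/1001 = 0.016, 48/1001 = 0.048 or 66/1001 = 0.066. In a family made up of more than 50 such p values, neither Bonferroni nor Holm can reject anything.

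**The case against.** Bonferroni is a valid method, and preferring a sharper one is not the same as finding an error. That stands, and it is why this point ranks low.

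The undefined family is the more basic gap: neither method can be carried out until the family and alpha are named. That also stands, and it shapes the fix, but it is no argument for the single-step version.

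Bonferroni also has simple matching simultaneous intervals, and the plan reports mean changes with 95% intervals. Holm has no equally simple counterpart, so a result significant under Holm may carry a Bonferroni-level interval that includes zero. This is a real but small cost.

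The all-three figures assume that every effect is real, which is the favourable case; the other rows of the table show how quickly the gain shrinks.

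A reader might infer that a step-down max-T adjustment could be read off the bootstrap already in the plan, and so exploit the correlation between outcomes at no extra work. The documents do not support this. Max-T needs resamples drawn by patient, shared across all outcomes, centred on the null and respecting visits and matching. Section 6 reports only 1000 resamples. Therapy need is a survival analysis, and no bootstrap test is assigned to the complication prevalences. Control of the family-wise error would also be approximate.

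Finally, the plan is written in the past tense, follow-up ended in July 2021 and the reference list includes a 2022 paper. Changing to a more liberal rule after seeing results must be disclosed.

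**Conclusion.** The point holds as a low-cost improvement. That Holm dominates Bonferroni for testing is a matter of proof and needs no trial figures beyond valid p values. The size of the benefit depends on the assumed 80% unadjusted power, correlation 0.3 to 0.5 and family size. It is about 8 points of average power and 17 to 19 points in the chance of supporting all three key outcomes when all three are real, about 3 points of average power with 8 of 16 real, and essentially nothing when one is real.

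Two stronger inferences should be resisted. Holm does not undo the growing cost of correcting for many outcomes, since its gain does not rise steadily with m. Nor does it help the primary outcome if that is tested alone outside the family. Nothing here makes the Bonferroni results invalid.

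**What to change.** State which outcomes and follow-ups form the family, whether the primary outcome belongs to it, and the alpha. Then replace the Bonferroni sentence with: p values within that family are adjusted by Holm's step-down method.

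Add three qualifications:

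- Adjusted intervals, if shown, stay at the Bonferroni level, with a note that they may include zero for a Holm-significant result.
- If the family holds more than about 50 bootstrap p values, use more than 1000 resamples.
- Step-down max-T may be offered only if a joint, patient-level, null-centred bootstrap of every outcome in the family is run.

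If results are already known, label the Holm analysis as post hoc and show the Bonferroni results beside it.

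Once the family is defined, the cost is one sentence and one line of code. Defining the family takes more thought, but the present Bonferroni sentence needs it as well. No new data or change of model is required.

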7.1 Adverse events (AEs)

We defined AE as undesirable experience of patients during the study. All AEs were reported by the patients or observed by the research team. Each AE will be recorded.

